8.1 Product characteristics

The Biosure Regenesorb Interference Screw, an absorbable screw designed with an open structure and made of biocomposite material, is used to fix ligaments, tendons, soft tissues or bone-tendon-bone grafts in knee surgery. Its manufacturing material is made of PLGA, β -TCP (β -tricalcium phosphate) and calcium sulfate. As compared with other absorbable screws made of other absorbable materials, its open structural design enables rapid bone ingrowth to make the screw integrated with bone tissue so as to promote healing. It has the following characteristics:

Bone ingrowth

- Its open structural design facilitates bone ingrowth.

Advanced materials

- In the pre-clinical study, the Biosure REGENESORB Interference Screw was replaced with bone within 24 months, but the control product BIOSURE HA Interference Screw was absorbed in a relatively longer time and might not be completely absorbed within 3~5 years.

Performance

- Excellent pullout resistance: Its fixation strength is similar to that of solid absorbable screws.
- BIOSURE Driver fully supports screws, maintains screw integrity and minimizes the possibility of breakage.

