9.4 Potential adverse reactions

As with any surgery, this surgery will cause risks. Potential complications of such implantation surgery include, but not limited to, anesthetic complications, pain at the incision and surgical sites,

Confidential and Proprietary

This document contains confidential and proprietary information on Smith & Nephew PLC and Smith & Nephew, Inc. and is only available to Smith & Nephew and its manufacturers. Without prior written approval of Smith & Nephew, the content cannot be replicated, printed totally/partially or disclosed in any other way, and anyone must use it as per the requirements, either expressed or implied by Smith & Nephew.

Study Protocol - Device	Smith+Nephew
A Prospective, Multi-center, Randomized Clinical Study to Evaluate the Safety and Effectiveness of Biosure Regenesorb Interference Screw in Arthroscopic Reconstruction of Cruciate Ligaments in Chinese Patients	Study No.: BIOSURE RG.SMD.PMA.2019.01
	Version: V2.0/July 3rd, 2020
	Page 24 of 74

surface and deep infections, bone injury or fracture, damage to surrounding tissues or blood vessels, embolism or coagulation problems (e.g., pulmonary embolism and deep vein thrombosis), nerve injury or stroke, treatment or implantation failure and surgery or treatment related complications requiring secondary surgical intervention. The expected adverse reactions are mild inflammatory reaction, foreign body reaction, deep and superficial infections and anaphylactic reaction.

10 Overall design

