10.1.6.2 Safety evaluation contents

Safety evaluation includes the following contents:

- Incidence (%) and frequency (number of events) of AEs related to device;
- Incidence (%) and frequency (number of events) of adverse events;

Confidential and Proprietary

This document contains confidential and proprietary information on Smith & Nephew PLC and Smith & Nephew, Inc. and is only available to Smith & Nephew and its manufacturers. Without prior written approval of Smith & Nephew, the content cannot be replicated, printed totally/partially or disclosed in any other way, and anyone must use it as per the requirements, either expressed or implied by Smith & Nephew.

Study Protocol - Device	Smith+Nephew
A Prospective, Multi-center, Randomized Clinical Study to Evaluate the Safety and Effectiveness of Biosure Regenesorb Interference Screw in Arthroscopic Reconstruction of Cruciate Ligaments in Chinese Patients	Study No.: BIOSURE
	RG.SMD.PMA.2019.01
	Version: V2.0/July 3rd, 2020
	Page 33 of 74

- Incidence (%) and frequency (number of events) of device deficiencies;
- Reoperation rate.

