16.3.3 Causal relationship between AEs and the device and its evaluation criteria

The AE is set to be related to the device in case of being "extremely probably related", "definitely related" and "probably related"; in case of other classification, the AE is set to unrelated to the device.

Classification	Description
Definitely un-related	The AE is identified as a result of a concomitant disease or the effects of another device/drug and is not related to the investigational product.
Probably un-related	The AE is more probably caused by other reasons and will not be improved or its prognosis is difficult to be judged after device withdrawal. Its recurrence is not found or difficult to be judged after device reuse.
Probably related	The occurrence of the AE meets the reasonable time sequence upon device use. The AE may be caused by the device or other reasons. It is improved

Confidential and Proprietary

This document contains confidential and proprietary information on Smith & Nephew PLC and Smith & Nephew, Inc. and is only available to Smith & Nephew and its manufacturers. Without prior written approval of Smith & Nephew, the content cannot be replicated, printed totally/partially or disclosed in any other way, and anyone must use it as per the requirements, either expressed or implied by Smith & Nephew.

Study Protocol - Device	Smith+Nephew
A Prospective, Multi-center, Randomized Clinical Study to Evaluate the Safety and Effectiveness of Biosure Regenesorb Interference Screw in Arthroscopic Reconstruction of Cruciate Ligaments in Chinese Patients	Study No.: BIOSURE RG.SMD.PMA.2019.01
	Version: V2.0/July 3rd, 2020
	Page 58 of 74

	after device withdrawal.
Extremely probably related	The occurrence of the AE meets the reasonable time sequence upon device use. The AE is more reasonably attributed to the used device than other reasons. It is improved after device withdrawal.
Definitely related	The occurrence of the AE meets the reasonable time sequence upon device use. The AE is more reasonably attributed to the used device than other reasons. The AE mode is consistent with the previously known mode caused by the device. The AE is improved after device withdrawal but appears after device reuse.

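### All three device-related grades in 16.3.3 require improvement after device withdrawal, which is not normally observable for an implanted absorbable screw, so device-related AEs may be unclassifiable or under-counted

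*Combined protocol and SAP*

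**What the plan says.** Section 16.3.3 has five causality grades. Three count as related (probably, extremely probably, definitely); otherwise, "in case of other classification, the AE is set to unrelated to the device".

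The withdrawal condition is part of every related grade. Extremely probably related ends "It is improved after device withdrawal", and probably related carries the same condition across a page break. Definitely related adds recurrence: "The AE is improved after device withdrawal but appears after device reuse".

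Probably un-related is the only grade that allows for an unobservable course, in these words: "The AE is more probably caused by other reasons and will not be improved or its prognosis is difficult to be judged after device withdrawal". It makes a similar allowance for recurrence after reuse.

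On the device, section 9.3 says it is for single use. Section 8.1 reports that, pre-clinically, "the Biosure REGENESORB Interference Screw was replaced with bone within 24 months", and that the control screw takes longer. Section 9.4 lists the expected reactions: "mild inflammatory reaction, foreign body reaction, deep and superficial infections and anaphylactic reaction".

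Section 10.1.6.2 puts first among its safety contents "Incidence (%) and frequency (number of events) of AEs related to device". Section 10.1.6.1 makes the safety analysis descriptive, without hypothesis tests.

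**The concern.** Withdrawal and rechallenge are usable causality criteria for a product that can be stopped and restarted. This screw stays in bone and is resorbed. Removing it takes another operation, and a single-use screw is not put back. Section 16.3.3 offers no alternative wording for a device left in place.

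What is at stake is the first listed safety indicator. With no test on safety, the reported count of device-related AEs is itself the evidence. The reactions expected in 9.4 are the ones the indicator ought to capture, and they may well occur around a screw that is never removed. Section 16.3.1 also ties AE follow-up after a subject completes the study partly to relatedness, and it does so with the term *possibly* related, which is not a grade on the scale.

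**Working it through.** The plan states no figure on this point, so the check is a reading of each grade against one case: an AE that the investigator attributes to a screw still in place.

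| Grade (16.3.3) | Counts as | Cause and timing | After withdrawal | After reuse | Does the case fit? |
|---|---|---|---|---|---|
| Definitely un-related | Unrelated | Another disease, device or drug | – | – | No: attributed to the screw |
| Probably un-related | Unrelated | Another cause more probable | No improvement, or cannot be judged | Not seen, or cannot be judged | No: attribution condition fails |
| Probably related | Related | Timing fits; device or another cause | Improves | – | No: withdrawal not observed |
| Extremely probably related | Related | Timing fits; device more reasonable | Improves | – | No: withdrawal not observed |
| Definitely related | Related | As above, plus known pattern | Improves | Reappears | No: neither observed |

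Three things follow.

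1. The withdrawal condition alone blocks the related grades. Reuse appears only in the highest of them, so it cannot by itself move an AE from related to unrelated.
2. Probably un-related joins its two parts with *and*. An AE attributed to the screw meets the second part (cannot be judged) but not the first (another cause more probable).
3. The case fits no grade, and the section does not say what to do with it. A site must either disregard the withdrawal clause, giving a related grade, or disregard the attribution clause, giving an unrelated one.

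**Illustration under assumed values only.** The one input from the documents is 70 subjects per arm (10.1.4.9). Let p be the true proportion of subjects with a device-related AE, and s the share of those whose AE ends up counted as related. Both are assumptions. Take one event per affected subject.

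- Expected number affected per arm = 70 × p
- Expected number counted = 70 × p × s
- Chance of counting none = (1 − p × s)^70

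| p | Affected | s = 0.1: counted; chance of none | s = 0.5: counted; chance of none | s = 1: chance of none |
|---|---|---|---|---|
| 2% | 1.4 | 0.14; 0.869 | 0.70; 0.495 | 0.243 |
| 5% | 3.5 | 0.35; 0.704 | 1.75; 0.170 | 0.028 |
| 10% | 7.0 | 0.70; 0.495 | 3.50; 0.028 | 0.001 |

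For example, p = 5% and s = 0.1 gives (1 − 0.005)^70 = 0.704. The documents fix neither p nor s, and s could be close to 1 if sites grade on timing and attribution. The table shows only that an arm of 70 is small enough for the grading practice to decide whether any device-related AE is reported.

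**The case against.** The strongest reply is that nothing in the table forces an AE caused by the screw into an unrelated grade. Probably un-related needs another cause to be more probable, and an investigator who blames the screw can still choose a related grade on timing and attribution. This stands. A reader might infer that device-related events will fall into the unrelated class, or that the reported rate will be driven towards zero. The text supports neither as a certain outcome. What it shows is a gap with a risk of under-counting. But choosing a related grade in this way means setting aside a written condition, and nothing ensures that the roughly four sites would do so alike.

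Removal is also possible. Reoperation is recorded at every visit from 6 weeks onwards and is itself a safety indicator, and section 7 mentions revision surgery. So withdrawal can be observed in some subjects, but it is not a routine step after an AE.

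The information is partly captured elsewhere. All AEs, device deficiencies and reoperations are summarised whatever their cause (10.1.6.2), and imaging observations go on the CRF (10.1.5.2, 10.2.2.9). The definition of an adverse device effect in 16.1 has no withdrawal condition, and SAE reporting in 16.3.1 and 16.3.2 does not depend on this scale. These limit the harm. They do not repair the device-related count, because 16.3.3 is the section that sets the related/unrelated split.

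**Conclusion.** The concern holds as a mismatch between the scale and the device. Improvement after withdrawal is part of every related grade and cannot normally be observed for this screw unless it is removed. Read literally, an AE attributed to a retained screw has no grade, so the device-related count may be incomplete or may depend on how each site resolves the gap.

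The size cannot be derived from the documents. They give no expected rate of device-related AEs and no removal rate, so the illustration rests wholly on its assumed p and s.

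A reader might also infer a bias between arms, since the investigational screw is described as resorbing sooner than the control and resorption could be taken for withdrawal. The documents nowhere equate the two, and the same scale applies to both arms, so that reading is not established.

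The effect is confined to a descriptive safety indicator and to the follow-up rule that uses relatedness. The primary non-inferiority conclusion and the total AE and SAE reporting are untouched. The point should be corrected because the indicator is listed first and the repair is small.

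**What to change.** In 16.3.3:

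- Keep the criteria already there as the basis for grading: time sequence, attribution to the device against other causes, and known reaction pattern. Link the last of these to the expected reactions in 9.4.
- Make improvement after withdrawal supporting evidence, used only when the screw has actually been removed.
- Delete the reuse criterion.
- State that being unable to judge the course after withdrawal does not by itself make an AE unrelated.

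In 16.3.1, reconcile the possibly/definitely related wording with the grades of the scale.

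The cost is a small revision of one table and the AE form, and brief retraining of sites. The reported device-related AE rate may be higher as a result.

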16.3.4 Causal relationship between AEs and surgery and its evaluation criteria

The AE is set to be related to the operation in case of being "extremely probably related", "definitely related" and "probably related"; in case of other classification, the AE is set to unrelated to the operation.

Classification	Description
Definitely un-related	The AE is identified as a result of a concomitant disease or the effects of another device/drug and is not related to the operation.
Probably un-related	The AE is more probably caused by other reasons and will not be improved or its prognosis is difficult to be judged in case of no operation/upon operation. Its recurrence is not found or difficult to be judged in case of operation.
Probably related	The occurrence of the AE meets the reasonable time sequence of operation. The AE may be caused by the operation or other reasons. It is improved upon operation completion.
Extremely probably related	The occurrence of the AE meets the reasonable time sequence of operation. The AE is more reasonably attributed to the operation than other reasons. It is improved upon operation completion.
Definitely related	The occurrence of the AE meets the reasonable time sequence of operation. The AE is more reasonably attributed to the operation than other reasons. The AE mode is consistent with the previously known mode

Confidential and Proprietary

This document contains confidential and proprietary information on Smith & Nephew PLC and Smith & Nephew, Inc. and is only available to Smith & Nephew and its manufacturers. Without prior written approval of Smith & Nephew, the content cannot be replicated, printed totally/partially or disclosed in any other way, and anyone must use it as per the requirements, either expressed or implied by Smith & Nephew.

Study Protocol - Device	Smith+Nephew
A Prospective, Multi-center, Randomized Clinical Study to Evaluate the Safety and Effectiveness of Biosure Regenesorb Interference Screw in Arthroscopic Reconstruction of Cruciate Ligaments in Chinese Patients	Study No.: BIOSURE RG.SMD.PMA.2019.01
	Version: V2.0/July 3rd, 2020
	Page 59 of 74

	generated in the operation. The AE is improved upon operation completion but appears in case of re-operation.
--	---------------------------------------------------------------------------------------------------------------

16.3.5 Device Deficiency

The device deficiency is defined as unreasonable risk occurred under normal use of medical device during the clinical trial, which may do harm to the human health and life safety, such as label error, quality problem and fault.

The investigators should timely report the device deficiency to the Sponsor and evaluate results of device deficiencies. The device deficiencies that may cause severe adverse events need to be reported as required by the GCP.

Device deficiencies must be observed intra-operatively and post-operatively, e.g. screw breakage.

17 Protocol Amendment and Protocol Deviation

17.1 Protocol Amendment

If neither the investigator nor the Sponsor has reached an agreement, either party is prohibited from modifying the protocol. Only after consulting and agreeing to amend, the protocol can be revised. Protocol amendment may affect the scientificity, or infringe the rights, safety or health of subjects, which should be submitted to the regulatory authorities and EC for approval before the implementation of the protocol amendment.

17.2 Protocol Violation by Individual Subjects in Emergency

An individual subject is allowed to violate the protocol only if measures are required to be taken to protect the life or physical health of the subject in an emergency, and such violation is limited to this subject. The investigator or other attending physician handling the situation should inform the EC and call the clinical study manager of Smith & Nephew (within 48 hours) (see study contact on page 13). If the study manager cannot be contacted, the investigator should contact the second contact of the Sponsor; see page 13 for details.

The investigator and Smith & Nephew should decide whether the subject who violates the study protocol can continue to participate in the study. Any protocol violations will be recorded in the written report of the investigator. The investigator should send the report and the reasons for the

Confidential and Proprietary

This document contains confidential and proprietary information on Smith & Nephew PLC and Smith & Nephew, Inc. and is only available to Smith & Nephew and its manufacturers. Without prior written approval of Smith & Nephew, the content cannot be replicated, printed totally/partially or disclosed in any other way, and anyone must use it as per the requirements, either expressed or implied by Smith & Nephew.

Study Protocol - Device	Smith+Nephew
A Prospective, Multi-center, Randomized Clinical Study to Evaluate the Safety and Effectiveness of Biosure Regenesorb Interference Screw in Arthroscopic Reconstruction of Cruciate Ligaments in Chinese Patients	Study No.: BIOSURE RG.SMD.PMA.2019.01
	Version: V2.0/July 3rd, 2020
	Page 60 of 74

violation (including the relationship with the therapeutic use of the device) to EC and Smith & Nephew. The EC can also determine that the subject should not continue to participate in this study.

17.3 Protocol deviation

Protocol deviation is defined as any case of non-compliance with the study protocol. Once the study site finds a protocol deviation, it should be reported to Smith & Nephew. According to the requirements, the investigator must also report the protocol deviation to the EC.

For protocol deviations, it is minimally required to report major protocol deviations, including GCP deviations, events affecting safety of subjects (inclusion/exclusion criteria), impact of examination or operation on study results, and the process of obtaining informed consent. A protocol deviation is judged as a major or minor one based on the information whether to affect the safety of subjects, whether to affect the study results and whether to affect obtainment of informed consent.

18 Access to Source Data/Documents

Each participating site will maintain appropriate medical and research records for this trial, in compliance with the Good Clinical Practice for Medical Device Clinical Trials and regulatory and institutional requirements. In order to protect the safety and rights and interests of the subjects, to ensure the authenticity, accuracy and integrity of the study progress and data, each study site should allow and cooperate with the Sponsor's monitors, quality assurance personnel, regulatory authorities and authorized representatives to perform quality review and audit. In order to complete the above activities, the above personnel should have the right to access, review or verify source data or source files.

Source data is all information, original records of clinical findings, observations, or other activities in a specific clinical trial necessary for the reconstruction and evaluation of the trial. These original documents and data records include, but are not limited to, inpatient or outpatient medical records, clinical and office charts, laboratory notes, memoranda, participants' memory aids or evaluation checklists, transportation, delivery, use and recovery records of the device, recorded audio tapes of counseling sessions, recorded data from automated instruments, copies certified after verification as being accurate and complete, microfiches, photographic negatives, microfilm or magnetic media, x-rays, and participant files and records kept at the pharmacy, at the laboratories, and ancillary departments involved in the clinical trial. The CRF for recording scales is saved as a source

Confidential and Proprietary

This document contains confidential and proprietary information on Smith & Nephew PLC and Smith & Nephew, Inc. and is only available to Smith & Nephew and its manufacturers. Without prior written approval of Smith & Nephew, the content cannot be replicated, printed totally/partially or disclosed in any other way, and anyone must use it as per the requirements, either expressed or implied by Smith & Nephew.

Study Protocol - Device	Smith+Nephew
A Prospective, Multi-center, Randomized Clinical Study to Evaluate the Safety and Effectiveness of Biosure Regenesorb Interference Screw in Arthroscopic Reconstruction of Cruciate Ligaments in Chinese Patients	Study No.: BIOSURE RG.SMD.PMA.2019.01
	Version: V2.0/July 3rd, 2020
	Page 61 of 74

document. The Adverse Event and Serious Adverse Event Report Form contains more information than medical records and should be considered as the source document. In the inpatient and outpatient medical record system of the hospital, the severity of adverse events and the causality judgments are usually not recorded, and there is a lack of records of correlation between the concomitant medication and adverse events. Therefore, the Sponsor will provide corresponding forms as source documents to save and record relevant information.

19 Finance and Insurance

19.1 Surgical instruments

After the Ethics Committee of the hospital approves the start of the clinical study, the Sponsor sends the investigational device to each study site. Only qualified personnel participating in this study is allowed to receive the investigational product. When the investigational device is delivered to each site, the complete inventory list should be provided. When there are any discrepancies between the contents recorded in the device transport form and the objects provided, they should be indicated on the transport form and immediately informed to the Smith & Nephew company. The device transport forms need to be kept in the folders of the study site. For any devices received, their quantity and size should be recorded in the device inventory log.

During the study process, the investigator must fully record the receipt, use, loss and disposal of the investigational product in the device study log to ensure that the storage and distribution of the investigational device is always under supervision. All device supplies must be stored in accordance with the conditions specified by the manufacturer, while complying with applicable regulatory requirements. The investigational device must be stored separately from the usual facilities/conventional items in the hospital. Until distribution prior to operation, all investigational devices must be stored in a safe locked area according to the conditions required in the instructions for use and only authorized personnel is allowed to enter.

It is the responsibility of the investigator to ensure that the investigational device inventory is sufficient and is only used for the subjects enrolled in this study. When the inventory is insufficient, the Sponsor should be contacted in advance. In addition, the Sponsor will coordinate as necessary to ensure supervision.

According to the instructions of the Sponsor, the investigator should return all remaining devices after completing the recruitment of subjects in this study.

Confidential and Proprietary

This document contains confidential and proprietary information on Smith & Nephew PLC and Smith & Nephew, Inc. and is only available to Smith & Nephew and its manufacturers. Without prior written approval of Smith & Nephew, the content cannot be replicated, printed totally/partially or disclosed in any other way, and anyone must use it as per the requirements, either expressed or implied by Smith & Nephew.

Study Protocol - Device	Smith+Nephew
A Prospective, Multi-center, Randomized Clinical Study to Evaluate the Safety and Effectiveness of Biosure Regenesorb Interference Screw in Arthroscopic Reconstruction of Cruciate Ligaments in Chinese Patients	Study No.: BIOSURE RG.SMD.PMA.2019.01
	Version: V2.0/July 3rd, 2020
	Page 62 of 74

